### **Mindfulness Based Cognitive Therapy (MBCT)**

Mindfulness is nonjudgmentally bringing awareness and acceptance to one's present-moment experience. Mindfulness-based interventions have demonstrated efficacy for treatment of diverse psychological symptoms including depression. To control for nonspecific factors in BATA including clinician contact, MBCT will be administered in an individual format. MBCT for individual treatment is empirically supported for a number of forms of psychopathology. Individualized adaptations of MBCT share primary components of the traditional program, including instruction and in-session practice of meditative exercises, didactics, and home practice. MBCT will be comprised of approximately 15 weekly 45-minute sessions. In the R33 phase, the number of sessions will match that of BATA. Sessions will begin with practice and discussion of a mindfulness meditation exercise, and then include: discussion of home practice, introduction to a new exercise and/or psychoeducational topic, and explanation of home practice for the coming week. Initial sessions will focus on practice and discussion of core meditation exercises to build mindfulness skills. Later sessions will focus on generalizing learned skills to cope with stressors and mood shifts. Psychoeducational content will center on identifying connections between negative thoughts, emotions, and sensations, recognizing triggers of emotional events, and developing an "action plan" to reduce stress-related symptoms. At the end of each session, participants will receive handouts that summarize the meditative exercise and/or psychoeducational content covered each week. Participants will also be asked to practice meditation exercises at home for 30 minutes each day and track practice time. Homework and logging are included to control for homework and monitoring components of BATA. Participants will receive guided meditation CDs (based on Segal et al.) to aid in home practice. Adherence will be monitored by tracking attendance; compliance of home practice will be monitored by evaluating frequency and duration of practice on weekly homework logs.

---

#### **6.1.2 DOSING AND ADMINISTRATION**

##### **MBCT/BATA Therapy Window Visits:**

Therapy sessions will be managed overall by calendar weeks, rather than trying to count days. This study is offering up to 15 weeks (as opposed to sessions) of treatment. Therapists will be instructed that they need to push to schedule at least one appointment per week, even if it's not on the same day of the week each week. The therapy portion of the study will follow this protocol:

Therapy Week	Procedures & Window
Week 0	The week the first MRI scan takes place. This "starts the clock" for both therapy and assessments
Weeks 1-3	Weekly therapy sessions. Sessions can start post-scan in week 0 if preferred; up to two sessions can be scheduled in a calendar week to make up missed sessions, with no more than three sessions completed by the end of week 3. Therapy content will not be skipped: for example, the content designated for Session 1 will be administered at the first therapy session, regardless of the week in which it takes place.
Week 4	Follow-up REDCap Questionnaires, computer tasks, and therapy. REDCap questionnaires and computer tasks will take place in this week as long as at least one session was attended in weeks 0-3. If 0 sessions were attended prior to this week, assessment is delayed to Week 5. If a subject has not attended at least one therapy session by the end of Week 4, they are a study drop by the 4-miss rule. This way every subject will have at least one "dose" (=therapy session) prior to the Wk4 visit.
Week 5	Weekly therapy session. If necessary, this can be a make-up for the Week 4 assessment if they did not attend or if Week 4 was first therapy session. If the participant does not attend therapy in Weeks 4 or 5, the "Wk4 Assessments" will not be collected and will be considered missing.
Weeks 6-7	Weekly therapy sessions. Up to two sessions per week can be conducted to make up previous missed appointments. No more than 7 Sessions will be delivered by the end of Week 7.
Week 8	Follow-up REDCap questionnaires, computer tasks, therapy, MRI Scan. If the subject has not attended at least 2 sessions overall, including at least 1 session in weeks 5-7, assessments and MRI scan may be delayed to Week 9. If a subject has not attended at least 1 session between weeks 5-8, they are a study drop by the 4-miss rule. Clinical response will be assessed and discussed with participants at this therapy session to determine if therapy is complete or will continue.
Week 9	Weekly therapy session. If necessary, this can be a make-up for the Week 8 visit and/or MRI Scan. If the participant does not attend therapy and/or MRI scans in Weeks 8 or 9, the "Wk8" assessments will not be collected and will be considered missing. DECISION POINT: The study team proposes that in terms of their best use of study resources, anyone who misses both the Week 4/5 and Week 8/9 Behavioral assessments, as well as the Week 8/9 MRI scan, should be considered a study drop and will be withdrawn from the study at that time.
Weeks 10-11	Weekly therapy sessions. Up to two sessions per week can be conducted to make up previous missed appointments. No more than 11 sessions will be conducted by the end of Week 11. If treatment is completed during one of these sessions, a final Assessment will be conducted at the final therapy session, and the final MRI scan will be scheduled by the end of the week following the final therapy session.

Week 12	Follow-up REDCap questionnaires, computer tasks, therapy, MRI Scan. If subject has not attended at least 3 sessions overall, including at least 1 session in weeks 9-11, assessments and MRI scan may be delayed to Week 13. If a subject has not attended at least 1 session between weeks 9-12, they are a study drop by the 4-miss rule.
Week 13	Weekly therapy session. If necessary, this can be a make-up for the Week 12 assessments and/or MRI Scan. If the participant does not attend therapy and/or MRI scans in Weeks 12 or 13, the "Wk12" assessments will not be collected and will be considered missing. DECISION POINT: Anyone who misses both the Week 8/9 and Week 12/13 Behavioral assessments, as well as the Week12/13 MRI scan, should be considered a study drop and will be withdrawn from the study at that time.
Week 14	Weekly therapy sessions. Up to two sessions per week can be conducted to make up previous missed appointments.
Week 15	Follow-up REDCap questionnaires, computer tasks, therapy, MRI Scan. If the subject has not attended at least 4 sessions overall, including at least 1 session in weeks 13-15, assessments and MRI scan may be delayed to the following week ("Week 16"). No therapy sessions will be held in Week 16.

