Although the utility of behavioral activation in treating suicidality has been hypothesized and supported in a case study, and MBCT has shown efficacy in reducing relapse of suicidality in individuals remitted from depression, more empirical support is necessary before using BATA or MBCT as the sole treatment for suicidal behavior. Therefore actively suicidal individuals will be excluded from the study at the intake assessment and throughout the trial.

Likewise, although both behavioral activation and MBCT have been found to improve a range of psychiatric symptoms and quality of life, they are not validated treatments for the full range of psychopathology that may present in our sample. Thus, symptom severity measures for depression, anxiety, and trauma-related symptoms will be administered every four weeks. If a participant shows a 10% or greater increase in symptom severity in any of those domains from baseline levels, he or she will be excused from the trial and referred for more intensive treatment and clinical management.

Following the conclusion of the trial, all participants will be provided with referral information as appropriate for further treatment.

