### 6.4 STUDY INTERVENTION COMPLIANCE

A participant will be considered a drop if they miss 4 therapy sessions in a row. Up to two sessions per week can be conducted to make up previously missed weeks. No more than 4 sessions will be completed before week 4, no more than 7 sessions will be complete before week 7, no more than 11 sessions will be complete before week 11. At week 8 onward, clinical response WILL be assessed and discussed with participant to determine if therapy is complete or will continue. No Therapy sessions will be held in wk 16.

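### The Week 5, 9 and 13 rows tie the depression, anxiety and trauma questionnaires to therapy attendance, so a few retained participants have no score for the 10% removal rule until Week 8 or 9

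*Combined protocol and SAP*

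**What the plan says.** Section 2.3.3 states that "symptom severity measures for depression, anxiety, and trauma-related symptoms will be administered every four weeks". A participant with a "10% or greater increase in symptom severity in any of those domains from baseline levels" is to be excused and referred for more intensive care. The reason given is that neither therapy is validated for the full range of psychopathology that may present.

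Section 2.3.3 does not name the instruments. In Section 4.2 the natural matches are the BDI-II, BAI and PCL-5, all part of the Week 4, 8 and 12 REDCap set. Section 4.2 and footnote 2 of Section 1.3 allow that set to be completed in person or by remote survey invitation.

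The therapy-week table in Section 6.1.2 says what happens when a window is missed:

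- Week 5 row: "If the participant does not attend therapy in Weeks 4 or 5, the 'Wk4 Assessments' will not be collected and will be considered missing".
- Week 9 row: the Week 8 set is likewise not collected if the participant "does not attend therapy and/or MRI scans in Weeks 8 or 9".
- Week 13 row: the same applies to the Week 12 set for someone who "does not attend therapy and/or MRI scans in Weeks 12 or 13".

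Retention is governed by Section 6.4: "A participant will be considered a drop if they miss 4 therapy sessions in a row". The table adds that at least one session is needed by the end of Week 4 and at least one in Weeks 5 to 8.

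**The concern.** The 10% rule needs a current score to compare with baseline. The three rows do more than accept that a form may be missed: they direct that it not be collected, and the condition is therapy attendance (or, in the Week 9 and 13 rows, therapy and/or scan attendance), although the forms do not require a visit. The people affected have already missed two consecutive weeks of therapy and are still in the trial. They are not early drop-outs, who under Section 4.2 are asked back for a final visit with self-report questionnaires. For them, a stated participant-protection rule has nothing to act on for roughly one further assessment cycle.

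**Working it through.** **Inputs.** Four-weekly measures and the 10% rule (Section 2.3.3); window and cancellation rules (Section 6.1.2 table); four-miss drop rule (Section 6.4); 210 randomised (Section 3). The documents state no figure on this point to reproduce and give no attendance rate.

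**An example.** A participant attends Weeks 1, 2, 3, 6, 7 and 8. The longest run of misses is two, and both blocks contain a session, so the participant is retained. The Week 4 set is cancelled and the first post-baseline set comes in Week 8. A rarer case attends Weeks 1, 2, 3, 7 and 9. The longest run of misses is three, and the first set comes in Week 9.

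**Delay.** Against a Week 4 check, 8 − 4 = 4 weeks or 9 − 4 = 5 weeks.

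**Counting patterns.** Take attend/miss for Weeks 1 to 9, one session per week at most, ignoring Week 0 starts and make-up double sessions. There are 2^9 = 512 patterns, of which 401 satisfy the retention rules (416 if the four-miss rule is applied only through Week 8; the counts below do not change). With Weeks 4 and 5 both missed, a run of four misses is avoided only if Weeks 2 and 3 are not both missed, Weeks 3 and 6 are not both missed, and Weeks 6 and 7 are not both missed. Week 1 is free.

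- Week 3 attended: 2 (Week 2) × 3 (Weeks 6 and 7) = 6.
- Week 3 missed: Weeks 2 and 6 must be attended and Week 7 is free, giving 2.
- Total: (6 + 2) × 2 (Week 1) × 4 (Weeks 8 and 9) = 64.

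Of these 64, the first check is in Week 8 for 32 and in Week 9 for 16. The other 16 attend neither week and face the Week 9 withdrawal decision.

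**Frequency under an assumption.** Let each week be missed independently with probability p. The run conditions hold with probability (1 − p)(1 − p²) + p(1 − p)² = (1 − p)²(1 + 2p). Then

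P(first check in Week 8 or 9 after cancellation) = p² × (1 − p)²(1 + 2p) × (1 − p²).

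| p (assumed) | Calculation | Probability | Of 210 |
|---|---|---|---|
| 5% | 0.0025 × 0.99275 × 0.9975 | 0.0025 | 0.5 |
| 10% | 0.01 × 0.972 × 0.99 | 0.0096 | 2.0 |
| 20% | 0.04 × 0.896 × 0.96 | 0.0344 | 7.2 |
| 30% | 0.09 × 0.784 × 0.91 | 0.0642 | 13.5 |

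Most of these are Week 8 checks: at 10%, about 1.8 in Week 8 and 0.2 in Week 9; at 20%, about 6.0 and 1.2.

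**Later windows.** If the first set was done in Week 4 and Weeks 8 and 9 are missed, the next set comes in Week 12 or 13, which is 8 or 9 weeks after the last. If treatment ends in Weeks 10 or 11 the interval is 6 or 7 weeks, because "a final Assessment will be conducted at the final therapy session". If the Week 8 set was done in Week 8 and Weeks 12 and 13 are missed, the Week 15 assessment follows 15 − 8 = 7 weeks later.

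**The case against.** The best defence is that this is an ordinary missed-visit rule. Section 2.3.3 gives the planned schedule, Section 6.1.2 gives windows, and any scheduled measure can be missed. That would be a full answer if the forms needed a visit. They do not, so the tie to attendance is avoidable.

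The second argument is that oversight continues, and this largely stands. SHAPS and CGI-I are completed at each attended session (Section 4.2). Missed visits trigger contact and rescheduling (Section 7.3). Therapists meet their supervisor weekly to consider worsening (Section 8.1.6), and Sections 2.3.3 and 7.2 allow removal on clinical grounds. An affected participant must also return in Week 6 or 7 to be retained, so a therapist sees them before the Week 8 check. None of this supplies a depression, anxiety or trauma score to set against baseline.

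The third is that the numbers rest on an assumption. That is correct. The table tells therapists to aim for at least one appointment each week on any day, and nothing in the documents supports a rate as high as 30%.

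A reader might also infer that the table contradicts itself, since the Week 4 row says "REDCap questionnaires and computer tasks will take place in this week as long as at least one session was attended in weeks 0-3". The documents do not support that. The row reads naturally as a timing gate ensuring one session before assessment; the Week 5 row then provides the make-up week and the consequence of missing both. The tension is with Section 2.3.3, not between the two rows.

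**Conclusion.** The point holds as a minor safety-monitoring gap. For a retained participant who misses Weeks 4 and 5, the first score the 10% rule can use arrives in Week 8 or 9, which is 4 to 5 weeks after a Week 4 check. On the assumed independent weekly miss rates this concerns about 0.5 to 13.5 of 210 participants, and about 2 to 7 at rates of 10% to 20%. Absences that cluster would change these figures, as would make-up and Week 0 sessions, which the count ignores. It also takes BDI-II, BAI and PCL-5 to be the measures meant by Section 2.3.3.

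Two stronger readings should be resisted. One is that these participants go unmonitored: they do not, since only the numeric trigger is lost. The other is that efficacy results are compromised: the model for Aims 3 and 4 in Section 9.2 uses pre- and post-treatment time points, so a missing mid-treatment set affects neither power nor the primary analysis.

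**What to change.** In the Week 5, 9 and 13 rows of Section 6.1.2, exempt the BDI-II, BAI and PCL-5 from the instruction not to collect. Send the existing REDCap invitation in Weeks 4, 8 and 12 to every participant still in treatment, whatever their attendance, and pursue non-response through the missed-visit contact in Section 7.3. Keep computer tasks and scans tied to attendance, and flag questionnaires completed off therapy in the efficacy data.

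The cost is wording in three rows, a few extra reminders and forms to review, and a small number of flagged records. The surveys and remote route already exist, and Section 4.2 already emails the self-report forms when an in-person final visit is omitted. Some invitations will go unanswered, so the gap shrinks but does not close. The change does not restore the C-SSRS, which stays with the computer-task visit.

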## 6.2 PREPARATION/HANDLING/STORAGE/ACCOUNTABILITY

### 6.2.1 ACQUISITION AND ACCOUNTABILITY

BATA therapist training: Study therapists will include Duke LCSW- or PhD-level clinicians with experience in cognitive behavioral therapy. Duke PI, [name] will supervise weekly BATA training and supervision meetings. Additional supervision will be provided if manual adherence falls below a predetermined "redline." BATA training will include didactic seminars by [name] at UNC and two pilot training cases supervised by [name]. [name] will be the adherence rater for BATA in this study.

MBCT therapist training: Study therapists will be Duke experienced LCSW- or PhD-level clinicians with experience in mindfulness-based interventions. All therapists will have previous training as meditation instructors and a personal meditation practice. [name] will supervise weekly training and supervision meetings. Additional supervision will be provided when manual adherence scores fall below a predetermined "redline." Training for MBCT delivery will include didactic seminars by UNC's [name] and two pilot training cases supervised by [name]. [name] will serve as senior consultant and adherence rater for MBCT in this study.

#### Therapy Session Video and/or Audio Recordings & Treatment fidelity:

The study therapy sessions will be video and/or audio recorded to ensure that the study therapists are performing the therapy correctly. These video and/or audio recordings will be recorded directly onto the study therapist's Duke computer/laptop, using a USB connected web camera that is connected to the hard drive of that computer. The recordings do contain PHI and thus the Duke lab computer used for recording has been encrypted with PGP/Bitlocker. These video/audio files will be only temporarily stored on the local Duke computer and will be moved to Department of Psychiatry & Behavioral Sciences protected folder. These video and/or audio files will then be transferred by the Duke approved secure file-sharing program (Box) to UNC to the study specific folder on the CIDD server and will be managed & monitored by UNC IT. Thus, the recordings will no longer be stored at Duke. These therapy recordings will be used to assess study therapist adherence throughout the study. Drs. [name] & [name], as the study adherence raters, and on the UNC IRB protocol and the Duke IRB protocol as outside key personnel, will access these recordings via the study specific folder on the UNC server. They

will review a number of weekly therapy sessions and Likert-scale ratings will be made of competence and adherence to the specific session objectives in the treatment manuals. If therapist drift is detected from the specific therapy protocol, therapists will be given feedback and the problem will be corrected through supervision with either [name] or the specific therapy expert (i.e. Drs. [name] or [name]). Patient adherence will be measured through ratings of completion of therapy homework as well as through patient self-report (i.e. % they reported they completed). All therapy session recordings will be kept at UNC no longer than 7 years after the study completion date and at that time, will be destroyed.

### 6.3 MEASURES TO MINIMIZE BIAS: RANDOMIZATION AND BLINDING

Randomization assignment will be performed through a dynamic balancing protocol that will balance treatment assignment within groups of lower (20-30) and higher (31+) SHAPS scorers. We recognize that anhedonia is common in patients with major depression. To ensure a true transdiagnostic sample, we will monitor DSM diagnoses of enrolled subjects in both phases to ensure that no more than 40% in either phase meet DSM criteria for a current depressive episode. We will stratify groups based on SHAPS scores. **For the R33 phase**, we will no longer stratify groups based on SHAPS score as all participants will have SHAPS scores 30 or greater.

Unblinding does not apply to this study since study therapists and participants are aware of which group the participant is in for the therapy intervention.

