**Endpoints:**

*Primary Endpoints:*

*Imaging (7T) – Tasking based activation to Monetary Incentive Delay (MID) Task; Task based activation to Emotion Reactivity task (Hammer)  
Behavioral/Observational:-Probabilistic Reward Task (PRT) and EffortExpenditure for Reward Task (EEfRT); Changes in SHAPs scores pre/post treatment*

*Secondary & Exploratory Endpoints:*

*Imaging (7T)- Resting state connectivity  
Behavioral/Observational -CGI-I; Homework Completion (participation and clinician-rated); ecological momentary assessment of activation, mood, reward experiences. Passive location tracking (PLT) data via the MetricWire app for the EMA sub-study to compare distance traveled before and after both treatments as a secondary, exploratory measure of behavioral activation. Follow-up analyses will evaluate relations between motion tracking, behavioral, brain, and clinical measures of response to both treatments.*

*PET Aim1: Extract dynamic change in binding potential (BPND%) before, during and after the task and then comparing these values before and after treatment between treatment groups. PET Aim2: Correlations between changes in PET striatal binding potential magnitudes and changes in fMRI.*

Study Population:	This study will recruit participants with clinically significant anhedonia, who are 18-50 years old who are able to read & understand English, and who are seeking treatment.
Phase:	Phase I/II
Description of Sites/Facilities Enrolling Participants:	Recruitment and therapeutic intervention for the study managed by Duke University Medical Center, Department of Psychiatry and Behavioral Sciences and Duke PI ;Eligible participants based on the initial Duke study assessment consent at UNC-Chapel Hill in the Department of Psychiatry under UNC PI for all 7T imaging, EMA and optional PET Scans.

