**Aims 3, 4, and 5 pertain to all 210 participants randomized (n=105 to receive BATA and n=105 to receive MBCT).**

Aim 3: We predict that BATA will produce clinically and statistically significant improvements in anhedonia and functional outcomes that exceed those due to the comparison treatment.

Aim 4: We predict that BATA will improve behavioral indices of reward sensitivity.

Aim 5: To evaluate the effects of BATA versus a comparison treatment on neural response to rewards. We predict that, consistent with Aim 1, BATA will increase right CN activation during reward anticipation and decrease rACC activation during reward outcomes and that BATA will not decrease amygdala activation to threat, confirming the specificity of BATA for targeting these positive valence neural systems. This Aim will provide a replication and extension of Aim 1 findings with a larger sample and with an optimal treatment dose.

In the PET sub-study, Hypothesis 1- BATA, but not the comparison treatment, will result in increased phasic striatal DA release but will not influence background DA striatal tone. Hypothesis 2- that normalization of fMRI-derived mesocorticolimbic activation due to BATA specifically will be associated with increased phasic DA release but no change in background DA tone during incentive processing.

This is not a pilot study but rather a Phase I/II study. The R61 phase (Phase I) of the protocol is designed to provide preliminary data for the acceptability, identification of the optimal dose of BATA as well as the preliminary efficacy of BATA in subjects with anhedonia compared to those in the MBCT control group. Using the fMRI data, this phase of the study will test if BATA produces changes in neural responses to reward anticipation and reward outcomes that exceed changes in the MBCT group and does not impact neural responses to threat. As such, a small group (N = 60) of subjects will be in this blinded phase and they will complete up to a total of 4 fMRI scans (pre-treatment, week 8, 12 and post-treatment). The R61 study will be entering a no-cost extension at the end of the current project period to allow for completion of data collection for this phase. Due to limited funds, the number of scans obtained is being reduced from up to 4 scans to two scans (pre- and post-treatment.) for participants

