##### **Eligibility and diagnostic assessment measures:**

**1) The Columbia Suicide Severity Rating Scale (C-SSRS)** will be administered. Participants indicating "yes" on items 4 (Active Suicidal Ideation with Some Intent to Act, without Specific Plan) and/or 5 (Active Suicidal Ideation with Specific Plan and Intent) within the last month will be excused from the trial and referred to more intensive clinical management. The C-SSRS will be used during the initial assessment visit over the past 1 month and then used to assess "since the last study visit" at the in-person assessment visit, if applicable during COVID-19, and the weeks 4, 8, 12 therapy visits that include the computer tasks and the final therapy/post-treatment visit. During the 1-2 remote & in-person assessment screening visits, if the participant has a 4 or 5 on the CSSRS, they will no longer be eligible for the study as per inclusion/exclusion criteria. **COVID-19 Update:\*\*Please note that the conduct of the CSSRS with computer tasks at the inperson assessment visit, wks 4, 8, 12 and final visit and are contingent upon the building availability and approval of in-person visits either at Duke or UNC. If not available and approved, the computer tasks with CSSRS will be omitted until the study team have the appropriate approvals to do the tasks at an in-person visit. These omissions (skipping the inperson visit) will not be considered protocol deviations since the omissions are necessary to be able to open the study and begin to collect the main primary outcomes of imaging and therapy.**

**2)** The SHAPS will be repeated to verify a score of  $\geq 30$ , corresponding to clinically significant anhedonia. **If the SHAPS score is  $<30$ , the participant will be ineligible (R33 phase);**

**3)** Clinician's Global Impression Scale-Severity score (CGI-S) = 3 to assure a clinically impaired sample. If the CGI score is 2 or less, the participant will be ineligible;

**4)** The Structured Clinical Interview for DSM Disorders-5 Research Version (SCID-5-RV) will be administered to assess exclusionary conditions and to characterize the sample. Individuals with primary anhedonia but no DSM diagnosis will be included. Exclusionary axis I disorders include:

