### 5 STUDY POPULATION

#### 5.1 INCLUSION CRITERIA

##### Inclusion Criteria

- 1) 18-50 years old and treatment seeking and willing to be video and/or audio recorded for clinical structured interviews and weekly therapy sessions. Only those subjects who agree to video and/or audio record will be allowed in the study. All recordings will occur at the Duke site for the clinical screening interviews & weekly therapy sessions.
- 2) SHAPS scores  $\geq 30$ , corresponding to clinically significant anhedonia;
- 3) Clinician's Global Impression Scale-Severity score (CGI-S)  $\geq 3$  to assure a clinically impaired sample;
- 4) Seeking treatment for anhedonia (i.e., referred from an outpatient clinic or responded to an advertisement for anhedonia treatment; endorses desire for treatment during screening).

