### 5.3 SCREEN FAILURES

Screen failures are defined as participants who consent to participate in the clinical trial but are not subsequently randomly assigned to the study intervention or entered in the study.

Screen failures who did not meet inclusion/exclusion criteria at the first visit will be allowed to return to Duke to rescreen for the study up to a total of 3 times, if it is deemed appropriate (examples include SHAPS<30, UA drug screen is positive at screening but the subject doesn't meet criteria for abuse or dependence, CGI-S <3, C-SSRS items #4 or 5 as yes, current psychotropic medication use, positive urine pregnancy screen with delivery of child and female subject is eligible again, etc).

Any participant going over 4 weeks between the remote assessment and the 7T pre-treatment scan, will be considered a screen fail and not randomized and have the ability to rescreen at a later date (i.e. will sign another econsent, redo SHAPS, C-SSRS, UA drug screen [if possible during COVID times], all self-report, SCID5, THI and computer tasks [if possible & contingent on ability to have in-person visits]). Their NART will not be redone and can be used for the rescreen.

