**Aim 2:** We will analyze whether dose moderates treatment response via regression models that predict change in neural target (CN and dACC) activation from the number of sessions as an indicator of BATA dose. Hierarchical linear modeling where time-in-weeks is treated as a continuous variable nested within subject will provide parameter estimates of the linear, quadratic, and cubic functions for change over time in neural target engagement over the course of treatment. Standard evaluation (e.g., significant at  $p < .05$ ) will guide our selection of the most appropriate function. From these functions, we can estimate both the point in time where the change in target engagement is greatest and where it approaches 0, meaning minimal further improvement is anticipated. Although mid-treatment scans will occur at weeks 8 and 12, we will estimate change continuously so the optimal dosage is not restricted to one of those timepoints.

**Aims 3 and 4:** To evaluate the efficacy of BATA, relative to MBCT, for treating anhedonia, functional outcomes, and behavioral indices of reward sensitivity, we will test for differential change over time between those who receive BATA and those who receive MBCT post-treatment. We will use an intent-to-treat (ITT) analysis for patients who receive BATA relative to those who don't. The ITT model will be a repeated-measures ANCOVA with effects for treatment condition (BATA, MBCT), outcome measure (SHAPS, PRT, etc), time (pre-treatment, post- treatment) and their interactions. The interaction tests will assess mean differences at each time point as well as differences in the degree of change between the groups. This also provides tests of each group relative to their baseline scores. We will include gender and age as covariates in these models. \*\*We will also note any participants who were enrolled in the study and had PRT & EffRT reward tasks data omitted during COVID-19 times.

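### The SHAPS entry rule for the R61 phase is not stated and conflicts with the R61 randomisation strata, and the pooled Aim 3–5 models adjust for neither phase nor stratum

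*Combined protocol and SAP*

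**What the plan says.** **Entry rule.** Section 5.1 requires a SHAPS score of at least 30, described as "corresponding to clinically significant anhedonia", and attaches no phase to it. Section 5.3, on who may rescreen after failing, gives a score below the cut-off among its cases ("examples include SHAPS<30"), again without a phase. The Synopsis describes the population in the same terms but gives no score: "This study will recruit participants with clinically significant anhedonia".

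**Phase-specific text.** Section 4.2 has the SHAPS repeated to verify a score of at least 30, but tags the consequence of falling short: "the participant will be ineligible (R33 phase". Section 6.3 sets up dynamic balancing to "balance treatment assignment within groups of lower (20-30) and higher (31+) SHAPS scorers", then says of R33 that "we will no longer stratify groups based on SHAPS score as all participants will have SHAPS scores 30 or greater".

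**Analysis.** Section 4.1 states that "Aims 3, 4, and 5 pertain to all 210 participants randomized", and adds that the 210 come from both phases. For Aims 3 and 4, Section 9.2 specifies a repeated-measures ANCOVA with treatment, outcome measure, time and their interactions, and says "We will include gender and age as covariates in these models". For Aims 1 and 5 the covariates are motion parameters, gender and age. Neither model names phase or the SHAPS randomisation group, and no analysis limited to scores of 30 or above is planned.

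**The concern.** If everyone had to score at least 30, a 20–30 stratum would be almost empty by construction. If the stratum was real, R61 had a lower floor that the eligibility section does not show. Either way, a reader cannot tell from the plan who was eligible for the first 60 places.

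This reaches the analysis because SHAPS is the entry measure, the R61 balancing factor and a primary endpoint. The Aim 3 result from the pooled 210 would be described as applying to clinically significant anhedonia, although part of the sample may have entered under a different rule. The factor used to balance the R61 allocation is also left out of the models, so any variance it explains stays in the error term. If this is settled only after results are seen, the choice of population on a primary endpoint becomes post hoc.

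**Working it through.** **1. Can Sections 5.1 and 6.3 both describe R61?**
- Section 5.1 allows scores of 30 or more. The lower stratum in Section 6.3 covers 20 to 30. The overlap is the single score 30.
- A balancing factor whose lower level can hold only one score would serve no purpose, so the two sections cannot both be a full description of R61.
- Section 6.3 drops the factor in R33 because everyone will then score 30 or more. That reason makes sense only if this was not guaranteed before. The R33 tag in Section 4.2 points the same way.
- The better-supported reading is that R61 could admit scores below 30. No section states the R61 floor.

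**2. How many participants could this touch?**
- R61 has 60 participants and R33 has 150 (Sections 1.1 and 4.1): 60 + 150 = 210.
- Upper bound: 60/210 = 28.6%. Lower bound: 0. The documents give no R61 score distribution, so the range cannot be narrowed.

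**3. Does the plan's power figure reproduce?**
Inputs from Section 9.1: 65 completers per arm (N = 130), two time points (m = 2), correlation ρ = 0.35, α = 0.05. For the group-by-time interaction, λ = f²·N·m/(1 − ρ), with 1 and N − 2 = 128 degrees of freedom.
- f = 0.20: λ = 0.04 × 130 × 2/0.65 = 16.0; power 97.8% (stated 98%).
- f = 0.14: λ = 0.0196 × 130 × 2/0.65 = 7.84; power 79.4% (stated 80%).

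Both reproduce and are not in dispute.

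**4. What would a sensitivity analysis at 30 or above cost in power?**
Assume that excluded participants come out of the 130 completers in proportion to R61's share of the sample.
- None excluded: N = 130; power 97.8% at f = 0.20 and 79.4% at f = 0.14.
- Half of R61 excluded: N = 130 × (1 − 0.5 × 60/210) = 111.4; power 95.6% and 72.9%.
- All of R61 excluded (the extreme): N = 130 × (1 − 60/210) = 92.9; power 91.7% and 64.9%.

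**5. What would the design factor cost?**
Three levels use 2 degrees of freedom as a main effect and 2 more for the interaction with time, so 4 for a single outcome. Leaving aside the age and gender terms, the test of differential change goes from 128 to 126 error degrees of freedom. The interaction is the part that matters: in a pre–post model, a main effect alone shifts both time points together and does not adjust the change.

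**The case against.** The best defence is that Section 5.1 simply shows the current R33 rule without a phase label. The document carries dated updates throughout, Section 4.2 tags the exclusion below 30 as R33, and Section 6.3 explains why stratification stopped. That is probably what happened, and it makes the wording conflict minor in itself. It still leaves the R61 rule unwritten and the pooled models unchanged.

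Other points on this side stand:
- CGI-S of at least 3 and seeking treatment for anhedonia apply with no phase limit, so any R61 entrant below 30 would still have been judged clinically impaired and treatment-seeking.
- Pre-treatment SHAPS is already in the Aim 3 model as the first time point. It is not a stratum or phase term, but baseline is not ignored.
- Gender and age are the only covariates for Aims 3 and 4. Aim 5 also has motion parameters.

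A reader might infer more than the text allows in three ways:
- **That people below 30 were randomised.** The plan permits it, but contains no enrolment data.
- **That the BATA–MBCT comparison is biased.** Section 6.3 balances the arms within the SHAPS groups, so a different pattern of change among lower scorers would be expected to fall on both arms alike.
- **That lower scorers shrink the SHAPS effect by a known amount.** Section 4.4 cites an anhedonia reduction of about 40%, but from trials of behavioural activation for depression in mood-disorder patients and without naming the scale. It cannot be applied to R61 baselines that the plan does not report.

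**Conclusion.** The concern holds in a limited form. The SHAPS entry rule for R61 is missing, and Sections 5.1 and 5.3 do not fit Sections 4.2 and 6.3. By design, between 0 and 60 of the 210 pooled participants (0 to 28.6%) may have entered below the plan's own cut-off, and the Aim 3–5 models ignore both phase and the factor used to balance R61. What is affected is precision and the population to which the Aim 3 result can be attached.

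This rests on reading the R33 remarks in Sections 4.2 and 6.3 as evidence of a lower R61 floor. If R61 in fact required 30 or above, the entry question becomes one of wording, and the case for analysing by phase and randomisation group remains. It would be tempting to move the Aim 3 conclusion to participants scoring 30 or above. The documents do not support that step: they define the analysis as intent-to-treat on all 210, and changing the primary population this late would create its own problem.

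**What to change.** 1. **Sections 4.2, 5.1, 5.3 and 6.3:** reconcile them by stating the SHAPS entry rule actually applied in R61 and in R33. This is wording only and records what was done; it does not require choosing a new threshold.
2. **Section 9.2, Aims 3–5:** add a design factor with the levels actually randomised (R61 lower SHAPS, R61 higher SHAPS, R33) and its interaction with time. The cost is 4 degrees of freedom per outcome. If the outcome-measure factor is kept in one joint model, let these terms differ by outcome.
3. **Section 9.2, Aim 3:** keep the intent-to-treat analysis of all 210 as primary and prespecify a sensitivity analysis in participants with entry SHAPS of 30 or above. Define this set by the entry score and not by stratum, because a score of exactly 30 falls in the lower R61 stratum but meets the cut-off.
4. **Reporting:** give the number of R61 participants below 30 by arm, so that the 0-to-60 range is replaced by a count.

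No new data are needed. In the extreme case the sensitivity analysis keeps 91.7% power at f = 0.20 but only 64.9% at f = 0.14, so it should be read for consistency of the estimate and not as a second test.
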